community fitness and will be inclusive of all individuals with chronic health conditions. Physical activity and exercise guidelines recommend everyone, including those with chronic health conditions, strive for 150 minutes of moderate intensity aerobic exercise per week.¹ This study will contribute to the knowledge of how patients achieve recommended individual HR and moderate-high intensity zones during exercise.

Aim 1: Measure the extent to which monitoring and education regarding intensity is provided (1) before HR monitoring intervention, (2) when providers know HR monitoring is occurring but without visual feedback, and (3) with visual feedback of HR monitoring.

We hypothesize providers will modify their behavior in the number of times they ask about intensity, adjust session intensity or provide education regarding intensity when visual feedback is provided compared to no feedback, which will be further increased from pre-study baseline levels.

Aim 2: Determine the efficacy of using HR with visual feedback during rehabilitation to reach target intensity.

We hypothesize participants will have higher mean HR and increased time in their individualized target HR zones when given visual feedback compared to no feedback during group sessions.

Aim 3: Determine the safety of using Heart Zones technology in rehabilitation for increasing participant exercise intensity.

We hypothesize the technology will be safe without an increase in number of adverse events throughout their rehabilitation stay.

Aim 4: Assess patient acceptability, exercise self-efficacy and confidence following use of Heart Zones technology in rehabilitation sessions.

We hypothesize use of Heart Zones technology in group settings with feedback will increase participant self-efficacy and confidence in reaching higher exercise intensities, and will be well accepted. Furthermore, we hypothesize the use of Heart Zones will be feasible in at least 75% of patient's group sessions.

Aim 5: Explore the feasibility of submax exercise testing when completed 2 times to establish individualized training targets for individuals receiving inpatient rehabilitation.

We hypothesize submax exercise testing will be feasible to perform, safe and informative to clinicians to establishing individualized heart rate zones. We believe there will be a change pre to post in submax testing indicating improvement in patient's condition.

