Clinical providers have many options for submaximal (submax) aerobic capacity testing, although they are rarely used outside of cardiac rehabilitation. The 6 minute walk test which have been studied in a range of populations including heart failure, end stage lung disease, COPD, chronic renal failure, and older individuals.¹⁵ The recumbent stepper test has been shown to be able to predict VO₂ peak in healthy adults.¹⁶ For individuals with limited ambulatory or lower extremity motor function, an alternative to determine aerobic capacity is to use the arm crank ergometer.¹⁷

This study will facilitate the understanding of feasibility and safety of moderate to vigorous aerobic endurance exercise, based on individually set aerobic intensity zones carried out in a rehabilitation setting. It will also study if the behavior of the provider or participant changes when provided visual feedback of HR during sessions.

STUDY ENDPOINTS:

[figure not shown]
- To evaluate the safety of using Heart Zones technology in a rehabilitation model across the rehabilitation continuum by recording the incidence of adverse events.
- To demonstrate the feasibility of using Heart Zones during group sessions by measuring the incidence of session usage to missed sessions.
- To demonstrate the efficacy of using visual feedback of HR monitoring to achieve greater intensities during sessions compared to no visual feedback of HR.
- To analyze the effect of HR monitoring with visual feedback on therapist perception of acceptability, feasibility and appropriateness as well as participant exercise self-efficacy and confidence.
- To assess feasibility of submax exercise testing in the inpatient setting to establish individualized target training intensities and assess the change in submax testing when completed at 2 times points.

STUDY INTERVENTION(S) / INVESTIGATIONAL AGENT(S):

Heart Zones is a commercially available software platform that integrates feedback from several different commercially available HR sensors. The software platform displays HR and provides continuous biofeedback with ability to provide individualized programs to maximize individual and multi-person sustained effort. It has the capability to record session data for later review and analysis.

We are not evaluating safety or effectiveness of the Heart Zones software, rather assessing the effect of monitoring HR with visual feedback in a group setting.

STU#: 00216223

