 2. Baseline measures and information will be collected from patient and medical record which include demographic information including gender, DOB, height, weight, co-morbidities, prior level of function, medical complications or concerns (pressure injuries, falls etc), precautions, admission level of function based on QI mobility items

STU#: 00216223

and outcomes measures in electronic medical record, reason for admission to rehabilitation.

3. Intervention:

1. Group and individual physical or occupational therapy sessions that are focused on endurance training (using upper and/or lower limb activities) which is a part of standard care for appropriate patients.
2. The only addition to usual standard care is the addition of a HR monitor that syncs with the Heart Zones software platform with or without visual feedback. Subjects will wear the HR monitor on their less sensory/motor impaired upper extremity.
3. There will be a continuous rolling enrollment, so some participants will receive HR feedback first while others will receive it on their second week.
4. Timing
 - i. Inpatient: 1 week of visual feedback of HR during group sessions and 1 week they will receive no feedback on their HR/zones.
 - ii. Day rehabilitation or community fitness: 2 weeks of visual feedback of HR and 2 weeks of no feedback due to fewer sessions per week.
5. Session Monitoring and Feedback
 - i. We will ask participants to rate their level of perceived exertion by using the Borg RPE Scale (6-20) at baseline, mid, and post each group session.
 - ii. Participants will answer 2 self-efficacy and confidence questions at the end of each session, rated from 0-100%.
 - iii. Subject's HR data from each session will be transferred for storage on a password protected computer accessible by approved lab staff only in order to perform summative data analysis, including peak HR, time in target HR zone, and average HR for whole session and for endurance training portion of the session.
6. We will monitor for occurrence of adverse events during sessions by assessing physiologic response to exercise, incidence of falls, etc.

4. Midpoint

1. We will collect information from their electronic medical record including new medical complications or concerns, their current functional level based on QI mobility items and outcome measures completed.

5. Post

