- Risk of loss of confidentiality will be minimized by not including personal identifying information on forms (participant will be assigned a research study number) and by conducting data collection in a private setting.

POTENTIAL BENEFITS TO PARTICIPANTS

There is likely no direct benefit to participants. Participation in this study will help researchers understanding if the use of visual feedback of HR in a group setting is feasible, efficacious and acceptable as care provided in a group model is a standard in rehabilitation.

DATA MANAGEMENT AND CONFIDENTIALITY

The analytic plan follows from the aims and the hypotheses. Descriptive statistics will be used to describe the participants and the data. Statistical tests will be utilized to assess for differences in individual outcomes baseline, mid and post through paired t-tests or appropriate non-parametric tests in consultation with a statistician. Data regarding the aims below may be analyzed for group sessions, individual sessions, and combined.

Aim 1: The null hypothesis is that there is no different in therapist behaviors to monitor/progress intensity prior to study, without visual feedback, or with visual feedback of participant's HR.

Aim 2: The null hypothesis is that there will be no difference in participant's ability to reach target intensity between sessions in which visual feedback of HR is provided and sessions where there is no visual feedback.

Aim 3: The null hypothesis is that there will be no increase in number of adverse events related to the use of Heart Zones with and without visual feedback.

Aim 4: The null hypothesis is that there will be no difference in participant exercise self-efficacy and confidence in reaching appropriate intensity when using visual feedback to no visual feedback during sessions.

Aim 5: The null hypothesis is that there will be no difference between submax exercise tests completed at baseline compared to post.

STU#: 00216223

Aim 6: The null hypothesis is that the providers will not feel the technology is appropriate, acceptable or feasible to use in a rehabilitation setting.

Data will be transferred to and stored on Shirley Ryan AbilityLab's REDCap system.

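### Aim 3's hypothesis and its null both assert no increase in adverse events; with only difference tests and no margin, the formal comparison could support Aim 3 only by being non-significant

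*Combined protocol and SAP*

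**What the plan says.** Under Objectives, Aim 3 is to "Determine the safety of using Heart Zones technology in rehabilitation for increasing participant exercise intensity". Its hypothesis reads: "We hypothesize the technology will be safe without an increase in number of adverse events throughout their rehabilitation stay". Under Data Management and Confidentiality, the Aim 3 null is that "there will be no increase in number of adverse events related to the use of Heart Zones with and without visual feedback".

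The same section plans descriptive statistics for the data in general. For inference it plans tests for differences: "paired t-tests or appropriate non-parametric tests in consultation with a statistician". No test is assigned to Aim 3 specifically. Alpha, sidedness, a margin, an acceptable event rate and a rule for reading a confidence interval are all absent.

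The matching item under Study Endpoints is "To evaluate the safety of using Heart Zones technology in a rehabilitation model across the rehabilitation continuum by recording the incidence of adverse events". The intervention section says that the study is "not evaluating safety or effectiveness of the Heart Zones software, rather assessing the effect of monitoring HR with visual feedback in a group setting". Under Procedures Involved, the only change to standard care is the "addition of a HR monitor that syncs with the Heart Zones software platform with or without visual feedback".

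**The concern.** A difference test can produce evidence against its null, but it cannot produce evidence for it. When the null is what the investigators hope to show, rejection counts against them, and failure to reject is the only result left that could be read in their favour. Failure to reject is also what a small sample or rare events tend to produce.

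This matters because the study's central hypothesis is that feedback raises exercise intensity, and the risk section lists chest pain, shortness of breath and falls among the risks that go with exercise. If such events are uncommon, a non-significant comparison is likely even if feedback doubled their risk. A report that took that result as no increase would claim safety that the data do not show.

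**Working it through.** **Step 1: hypothesis against null, aim by aim** (Objectives against Data Management and Confidentiality).

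| Aim | Hypothesis | Null | Opposed? |
|---|---|---|---|
| 1 | Provider behaviour changes with feedback | No difference | Yes |
| 2 | Higher HR and more time in zone | No difference | Yes |
| 3 | No increase in adverse events | No increase in adverse events | No |
| 4 | Self-efficacy and confidence rise | No difference | Yes |
| 5 | Submaximal test changes from pre to post | No difference | Yes |
| 6 | Providers find it feasible and appropriate | That "the providers will not feel the technology is appropriate, acceptable or feasible to use in a rehabilitation setting" | Yes |

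The two Aim 3 statements differ in wording. The null mentions use with and without feedback, and the hypothesis mentions the whole stay. Their direction is the same.

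**Step 2: what each test result would mean.** Rejecting the Aim 3 null would indicate more events, which is against the hypothesis. Not rejecting it is compatible with no increase and also with an increase too small for the data to detect. Without a margin or an interval, the test does not separate the two.

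**Step 3: which contrast is available.** Participants wear the monitor in both the feedback and the no-feedback period. The only condition without the monitor is the Aim 1 baseline, which counts provider behaviours, not adverse events. A comparison can therefore address feedback versus no feedback, but not technology versus none.

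**Step 4: how uninformative non-significance could be.** The plan gives 90 completers with no derivation, so there is no power figure to reproduce. What follows is illustrative.

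Inputs:
- n = 90 pairs (participant population table), taking all 90 as observed in both conditions.
- Assumed: risk of any event without feedback p0 = 2%, 5%, 10% or 20%; risk with feedback p1 = 2 × p0; within-person correlation rho = 0 or 0.3; exact McNemar test at 5%.

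Formulas:
- p11 = p0·p1 + rho·√[p0(1 − p0)·p1(1 − p1)]
- b = p1 − p11 (event with feedback only); c = p0 − p11 (event without feedback only)
- Discordant pairs M ~ Binomial(90, b + c). Given M, the number with feedback only ~ Binomial(M, b/(b + c)). Power sums the probabilities of all outcomes that the exact test rejects in the direction of harm.

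Example, 5% to 10%:
- rho = 0: p11 = 0.05 × 0.10 = 0.005, b = 0.095, c = 0.045. Expected discordant pairs = 90 × 0.14 = 12.6; b/(b + c) = 0.679; two-sided power = 0.163.
- rho = 0.3: p11 = 0.005 + 0.3 × √0.004275 = 0.0246, b = 0.0754, c = 0.0254. Expected discordant pairs = 9.1; b/(b + c) = 0.748; two-sided power = 0.206.

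| Risk without → with feedback | Power, two-sided 5% (rho 0 / 0.3) | Power, one-sided 5% (rho 0 / 0.3) |
|---|---|---|
| 2% → 4% | 4% / 3% | 0.074 / 0.065 |
| 5% → 10% | 16% / 21% | 0.256 / 0.304 |
| 10% → 20% | 38% / 52% | 0.520 / 0.653 |
| 20% → 40% | 80% / 92% | 0.878 / 0.960 |

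The first row is low for a simple reason. Two-sided significance needs at least six discordant pairs, all in one direction (2 × 0.5⁶ = 0.031, whereas 2 × 0.5⁵ = 0.0625). Only about 90 × 0.0584 = 5.3 discordant pairs are expected at rho = 0.

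**Step 5: zero events.** If none of 90 participants has a given event, the two-sided 95% upper limit is 1 − 0.025^(1/90) = 4.0%, and the one-sided 95% limit is 1 − 0.05^(1/90) = 3.3%.

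**The case against.** The best reply is that a null of no increase is the ordinary null for detecting harm, and nothing in the documents says that the team will read non-significance as safety. That is true. A reader might infer that the protocol commits to such a conclusion, but it does not. What stands is narrower: Aim 3's own hypothesis is the absence of an increase, and the comparison as planned has no other way to support it.

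Incidence is also to be recorded and described, so part of the remedy is already planned. But description without an interval or an interpretation rule does not turn a non-significant test into evidence, and incidence during use has no monitor-free comparator. The offer to consult a statistician concerns which difference test to use; it does not supply a margin.

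Three stronger readings are not supported:
- That the paired t-test is the plan's test for Aim 3. The section ties its tests to baseline, mid and post outcomes, leaves the choice open, and assigns none to adverse events. The Aim 3 null does not even state cleanly that it contrasts feedback with no feedback.
- That the comparison is uninformative for every event. At 20% risk, power against a doubling is 80% to 92%. The risk list includes fatigue, muscle soreness and armband discomfort, which may be common.
- That withdrawals will bias the comparison by a known amount. The withdrawal section permits removal after transfer for higher-level monitoring or a longer acute hospitalisation, but the documents give no frequency and define no analysis set restricted to complete pairs. Losing serious first-period events is a reason to define the set, not a demonstrated bias.

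**Conclusion.** The point holds and should be fixed. Aim 3 is the only aim whose null repeats its hypothesis. With difference tests alone and no margin, its formal comparison could favour the aim only by failing to reject.

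The logic rests on the text and needs no assumption. The size does: event rates, a doubling, the correlation, the McNemar test and 90 complete pairs are all illustrative. On those assumptions, a two-sided test would miss a doubling about 96% to 97% of the time from a 2% risk, 79% to 84% from 5%, 48% to 62% from 10%, and 8% to 20% from 20%. Non-significance is thus close to uninformative for uncommon events and reasonably informative for common minor ones.

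None of this suggests that feedback is unsafe. Two secondary clarifications remain: the plan does not say whether session monitoring, record-based complications or both feed Aim 3, and the statement that software safety is not evaluated sits awkwardly with Aim 3 and its endpoint.

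**What to change.** Replace the Aim 3 null with estimation, for example: *Aim 3: we will report adverse events during monitored sessions with and without visual feedback, and the difference with a 95% CI that allows for repeated sessions per participant. We will state what increase the interval excludes and will not interpret a non-significant test as no increase.*

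Alongside it:
- Include everyone who wore the monitor at least once, and count events that led to withdrawal, so that serious first-period events are kept.
- Report complications taken from the medical record separately, since they may arise outside sessions and do not fit a per-session denominator.
- Limit the comparative conclusion to feedback versus no feedback, because the monitor is worn in both periods.
- If a claim of no increase is still wanted, set a margin before analysis and test against it.
- As secondary edits, name the event source for Aim 3 and reconcile the aim and endpoint wording with the software-safety statement.

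The cost is a rewording of Aim 3 and its analysis, plus the condition recorded for each session event; no extra visits or participants are needed. The downside is a more modest safety claim and wide intervals for rare events.

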1. At the end of the study, we will ask participants to answer one summative quality improvement question regarding their participation in the study.
 - i. If discharged unexpectedly, we will attempt to reach out to participants via their preferred contact method (phone or email) in order to allow them to provide feedback.
2. We will collect information from their electronic medical record including new medical complications or concerns, their current functional level based on QI mobility items and outcome measures completed and ask the participant regarding discharge destination.
3. If the submax exercise test was completed at baseline, we will complete the same test a second time at least 3 days later.

AIM 6:

- a. We will ask for provider feedback and perceptions at the end of the study by their completion of the Acceptability, Appropriateness and Feasibility Questionnaire.
- b. Given the potential for covering providers, we will only ask participation from participating providers who are core staff/covering for a long term placement at each of the study locations.

STU#: 00216223

SHARING RESULTS WITH PARTICIPANTS

Given the nature of the study design, participants will receive immediate continuous feedback of their heartrate for a portion of the study. Individual study results may be provided once the study is completed if the patient requests. Results will be shared in written or verbal means, depending on participant's preference.

STUDY TIMELINES

The participant will be in the study for up to the duration of their length of stay in inpatient rehabilitation or day rehabilitation. We anticipate that it will take up to 8 months to enroll all study participants and primary analyses will be completed by September 2022.

INCLUSION AND EXCLUSION CRITERIA

Participant Criteria:

Inclusion:

- Age 18-90 years
- Admitted to inpatient rehabilitation, day rehabilitation or participant in community fitness
- Qualifies for group therapy based on diagnosis and insurance reimbursement
- Physician clearance for participation

Exclusion:

- Unable to provide informed consent due to cognitive impairment
- Inability to communicate with investigators
- Sternal Precautions
- Individuals with LVADs
- Pregnant women
- Uncontrolled Hypertension
- Serious and unstable cardiac arrhythmias
- Loss of bilateral upper extremity sensation
- At high risk for skin breakdown due to poor skin integrity (open wound, fragile skin, etc)

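### Aim 3 compares numbers of adverse events with no exposure denominator, so the contrast can be biased if the order of conditions is unbalanced or early exit differs by order

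*Combined protocol and SAP*

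**What the plan says.** The protocol words the safety question in three ways.

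- Objectives, Aim 3: the technology is expected to be safe "without an increase in number of adverse events throughout their rehabilitation stay". This is a count over the whole stay.
- Study Endpoints: safety is evaluated "by recording the incidence of adverse events". The word suggests a rate or proportion, but the section does not say per what.
- Data Management and Confidentiality, Aim 3: the null hypothesis is "no increase in number of adverse events" attributed to Heart Zones, with and without visual feedback. This is a count, compared between conditions.

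Planned exposure is balanced within each participant (Procedures Involved, Aims 2-5, Intervention, Timing). Inpatients have "1 week of visual feedback of HR during group sessions and 1 week they will receive no feedback on their HR/zones". Day rehabilitation and community fitness participants have "2 weeks of visual feedback of HR and 2 weeks of no feedback due to fewer sessions per week". On order, the same section says only that, under rolling enrolment, "some participants will receive HR feedback first while others will receive it on their second week".

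Shortened participation is foreseen. Study Timelines caps participation at the length of stay. The Post section says: "If discharged unexpectedly, we will attempt to reach out to participants via their preferred contact method"; the purpose of that contact is to collect feedback. Withdrawal of Participants allows removal after transfer to higher-level monitoring or a prolonged acute hospitalisation. No rule covers an incomplete second block in the Aim 3 comparison. The only tests named are paired t-tests or non-parametric alternatives, chosen with a statistician.

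**The concern.** The Intervention section looks for adverse events during sessions. The expected number of such events under a condition is then the risk per session multiplied by the sessions attended under that condition. Early exit removes sessions from whichever condition came second. If more participants start with feedback than without, or if those who start with feedback leave early more often, the feedback condition keeps more sessions and shows more events at the same underlying risk. The reverse pattern could hide a real increase.

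Safety is a named aim, and the Study Summary records no data monitoring board. A contrast that partly reflects exposure could be read as reassurance or as a signal when it is neither.

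**Working it through.** **Inputs.** The documents give equal planned blocks, both orders in use, no order split and no rate of second-block loss. They also give no adverse event rate, alpha or power, so there is no Aim 3 figure of the plan's own to reproduce. Everything below rests on assumed values:

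- p = share of participants who receive feedback first;
- c = mean fraction of second-block exposure lost, with the first block taken as complete;
- equal true risk per unit of exposure in both conditions.

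**Formula.** In units of one full block per participant:

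- feedback exposure = p + (1 − p)(1 − c)
- no-feedback exposure = (1 − p) + p(1 − c)

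At equal risk the expected count ratio is the first divided by the second.

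| p | c | Feedback | No feedback | Ratio |
|---|---|---|---|---|
| 0.5 | 0.25 | 0.875 | 0.875 | 1.00 |
| 0.6 | 0.10 | 0.960 | 0.940 | 1.02 |
| 0.6 | 0.25 | 0.900 | 0.850 | 1.06 |
| 0.7 | 0.25 | 0.925 | 0.825 | 1.12 |
| 0.7 | 0.50 | 0.850 | 0.650 | 1.31 |
| 0.3 | 0.25 | 0.825 | 0.925 | 0.89 |

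At p = 0.5 the two expressions are identical, so the ratio is 1.00 for every c.

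**Loss that differs by order.** Balance in p is not enough if c depends on order. With p = 0.5, suppose feedback-first participants lose 25% of their second block and the others lose 10%. Feedback exposure is 0.5 + 0.5 × 0.90 = 0.950, no-feedback exposure is 0.5 + 0.5 × 0.75 = 0.875, and the ratio is 0.950/0.875 = 1.09.

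**In events.** Take 90 participants with one week per condition and an assumed 0.2 events per participant-week. At p = 0.6 and c = 0.25, exposure is 81.0 against 76.5 weeks, giving 16.2 against 15.3 expected events. At p = 0.7 and c = 0.25 it is 83.25 against 74.25 weeks, giving 16.65 against 14.85.

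**False-positive rate.** This uses an exact conditional binomial test of the counts against an even split (two-sided 0.05, assumed), with loss unrelated to order.

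| p, c | 20 events in total | 100 events in total |
|---|---|---|
| 0.5, 0.25 | 0.041 | 0.035 |
| 0.6, 0.25 | 0.043 | 0.043 |
| 0.7, 0.25 | 0.048 | 0.066 |
| 0.7, 0.50 | 0.078 | 0.220 |

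**With a denominator.** Dividing by exposure gives an expected ratio of 1.00 for every p and c, provided loss is unrelated to the events. When the same exact test uses the exposure share as its null value, its false-positive rate is between 0.021 and 0.047 over the values tried (20 to 200 events, c from 0.10 to 0.50, p from 0.5 to 1.0).

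**The case against.** The strongest reply is that the design already protects the comparison. Blocks are equal within participant, both orders occur, and losses unrelated to order cancel at an even split. If order fell like a coin toss, a split of 54:36 or more uneven among 90 would occur with probability of only about 0.07. With a split between 40:60 and 60:40 and up to 25% loss, the distortion is about 6% or less. This stands as a limit on size. It does not remove the point, because the protocol neither randomises order nor aims for balance.

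A reader might infer that the plan deliberately chose counts over rates. The documents do not support that. Study Endpoints speaks of incidence, and the next endpoint there uses the same word for session use relative to missed sessions. The fair criticism is that the sections differ in wording and none defines a denominator.

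A reader might also take 25% as the plan's own loss rate, from 120 consented and 90 completing (30/120). That does not follow. The 120 is a ceiling that also covers people screened, and screening and medical clearance come after consent. Some of the 30 may therefore never have a session in either condition. The 25% used above is purely illustrative.

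A paired test would omit anyone with no second block, so a wholly missing block would not distort it. That is correct, but it also drops people withdrawn for medical reasons, who matter most for safety. Partly completed second blocks would still enter with unequal exposure.

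Finally, sessions are not the natural denominator for every event. Objectives refers to the whole stay, and new complications are also gathered from the medical record at midpoint and post. This stands and is reflected in the fix.

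**Conclusion.** The concern holds as a possible bias. The Aim 3 hypothesis has no exposure denominator, the second block can be cut short, and order is left to rolling enrolment. Followed as written, the comparison can reflect exposure as well as risk.

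The size depends on two inputs that the documents do not give. It is nil at a 50:50 split with loss unrelated to order, about 6% at 60:40 with 25% of the second block lost, and about 12% at 70:30 with the same loss. The direction reverses when the no-feedback condition more often comes first. Larger distortions need heavier loss or greater imbalance, and nothing in the documents indicates either. With few events the effect on the false-positive rate is slight.

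A reader might infer that a false excess or deficit must result. The equal planned blocks and the use of both orders do not support that: a net bias needs an unbalanced order, or loss that differs by order. The change is still worth making, because it replaces an undefined measure at little cost.

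**What to change.** In Data Management and Confidentiality, and consistently in Objectives and Study Endpoints, define Aim 3 as adverse events during monitored sessions per session (or session-hour), by feedback condition. Include everyone who wore the monitor at least once.

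Report the rate ratio with a 95% confidence interval from a Poisson or negative binomial model, with log sessions as offset and clustering by participant. If events are few, use an exact conditional test whose null share is the feedback share of all monitored sessions. Also report the order split, sessions by condition and event-related withdrawals by condition. Report complications found only by record review separately.

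The cost is about one sentence in the analysis text and matching wording in the two other sections. The data are already planned: session use is a feasibility endpoint, heart rate data are stored for each session, and the privacy section lists number of sessions among the information drawn from the record.

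The limitation is that when an event itself ends participation, loss of exposure is informative and a rate does not fully correct for it. Listing event-related withdrawals by condition makes that visible but does not remove it.
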